#### **8.6.1.1 Progression-free Survival**

The non-parametric Kaplan-Meier method will be used to estimate the PFS curve in each treatment group. The treatment difference in PFS will be assessed by the stratified log-rank test (based on the stratification factors defined in Section 5.4). A stratified Cox proportional hazard model with Efron's method of tie handling will be used to assess the magnitude of the treatment difference (ie, the hazard ratio [HR]) between the treatment arms. The HR and its 95% CI from the stratified Cox model with Efron's method of tie handling and with a single treatment covariate will be reported. The stratification factors used for randomization (See Section 5.4) will be applied to both the stratified log-rank test and the stratified Cox model.

Since disease progression is assessed periodically, PD can occur any time in the time interval between the last assessment where PD was not documented and the assessment when PD is documented. For the primary analysis, for the subjects who have PD, the true date of disease progression will be approximated by the date of the first assessment at which PD is objectively documented as assessed by BICR per RECIST 1.1 modified to follow a maximum of 10 target lesions and a maximum of 5 target lesions per organ, regardless of discontinuation of study drug. Death is always considered as a confirmed PD event.

In order to evaluate the robustness of the PFS endpoint per modified RECIST 1.1 by central imaging vendor, we will perform 2 sensitivity analyses with a different set of censoring rules. The first sensitivity analysis is the same as the primary analysis except that data for any subject who misses more than one disease assessment (with or without a subsequent death or progression) are censored at the last disease assessment prior to missing visits. The second sensitivity analysis is the same as the primary analysis except that it considers discontinuation of treatment or initiation of an anticancer treatment subsequent to discontinuation of study-specified treatments, whichever occurs later, to be a PD event for subjects without documented PD or death. If a subject meets multiple criteria for censoring, the censoring criterion that occurs earliest will be applied. The censoring rules for primary and sensitivity analyses are summarized in [Table 11](#).

**Table 11 Censoring Rules for Primary and Sensitivity Analyses of Progression-free Survival**

Situation	Primary Analysis	Sensitivity Analysis 1	Sensitivity Analysis 2
No PD and no death; new anticancer treatment is not initiated	Censored at last disease assessment	Censored at last disease assessment	Censored at last disease assessment if still on study therapy; progressed at treatment discontinuation otherwise
No PD and no death; new anticancer treatment is initiated	Censored at last disease assessment before new anticancer treatment	Censored at last disease assessment before new anticancer treatment	Progressed at date of new anticancer treatment
No PD and no death; $\geq 2$ consecutive missed disease assessments	Censored at last disease assessment	Censored at last disease assessment prior to $\geq 2$ consecutive missed visits	Censored at last disease assessment
PD or death documented after $\leq 1$ missed disease assessment	Progressed at date of documented PD or death	Progressed at date of documented PD or death	Progressed at date of documented PD or death
PD or death documented at any time after $\geq 2$ missed disease assessments	Progressed at date of documented PD or death	Censored at last disease assessment prior to the $\geq 2$ missed disease assessment	Progressed at date of documented PD or death

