12. Laboratory tests for screening are to be performed within 10 days prior to the first dose of trial treatment, with the exception of hepatitis serologies which may be performed within 28 days of the first dose of trial treatment. Testing for Hepatitis B and Hepatitis C should be performed as mandated by the local health authority. Starting with Cycle 1, laboratory safety tests must be conducted within 72 hours prior to the first dose of trial treatment in each cycle, with the exception of the thyroid function tests and LDH, which may be conducted up to 10 days prior to first dose of trial treatment. Laboratory results must be known prior to dosing.
13. Urinalysis is to be repeated every 6 cycles beginning at Cycle 6.
14. Thyroid tests are to be repeated every 2 cycles beginning at Cycle 2.
15. This sample should be drawn for planned analysis of the association between genetic variants in DNA and drug response. If there is either a documented law or regulation prohibiting collection, or if the IRB/IEC does not approve the collection of the sample for these purposes, then this sample will not be collected at that site. If the sample is collected, leftover extracted DNA will be stored for Future Biomedical Research if the subject signs the Future Biomedical Research consent. If the planned genetic analysis is not approved, but Future Biomedical Research is approved and consent is given, this sample will be collected for the purpose of Future Biomedical Research.
16. CT with contrast (preferred) of the chest, abdomen and pelvis is required for all subjects; non-contrast CT of the chest and MRI of the abdomen and pelvis may be used for subjects in whom iodinated contrast is contraindicated.
17. Tumor imaging to be performed every 6 weeks ( $42 \pm 7$ ) days for the first 48 weeks of treatment from the date of randomization, then every 9 weeks ( $63 \pm 7$ ) days subsequently until documented disease progression, or the start of new anti-cancer treatment. Refer to Section 7.1.2.7 for additional details. Imaging is to follow calendar days regardless of any delays in dosing. For patients treated beyond progression of disease as verified by BICR, the timing of imaging should continue from the date of randomization (every 6 weeks ( $42 \pm 7$ ) days) for the first 48 weeks, then every 9 weeks ( $63 \pm 7$ ) days) or at shorter intervals, as deemed necessary by the investigator).

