#### **7.1.2.7.2 Tumor Imaging During the Trial**

The first on-trial imaging assessment should be performed at 6 weeks ( $42 \pm 7$  days) from the date of randomization. Subsequent tumor imaging should be performed every 6 weeks ( $42 \pm 7$  days) for the first 48 weeks of treatment, then every 9 weeks ( $63 [\pm 7]$  days), or more frequently if clinically indicated. Timing of tumor imaging should follow calendar days and should not be adjusted for delays in cycle starts. (Note: the date imaging is performed is the date of the imaging, not the date the images are reviewed.) Imaging should continue to be performed until disease progression verified by BICR (unless site PI elects to continue treatment and follow irRECIST), the start of a non-study anti-cancer treatment, withdrawal of consent, or death, whichever occurs first. Supplemental imaging must be submitted to the central imaging vendor if it shows evidence of progression or if it is used to support a determination of PR or CR.

Per RECIST 1.1 (modified to follow a maximum of 10 target lesions and a maximum of 5 target lesions per organ), PR and CR should be confirmed by a repeat tumor imaging assessment not less than 4 weeks from the date the response was first documented. The tumor imaging for confirmation of response may be performed at the next scheduled tumor imaging (ie, 6 or 9 weeks later), whichever is clinically indicated. Subjects will then return to regular scheduled imaging every 6 or 9 weeks, starting with the next scheduled imaging time point. Subjects who obtain confirmatory imaging do not need to undergo the next scheduled tumor imaging if it is <4 weeks later; tumor imaging may resume at the subsequent scheduled imaging time point.

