### **7.1.2.7.3 End of Treatment and Follow-up of Tumor Imaging**

For subjects who discontinue trial treatment, tumor imaging should be performed at the time of treatment discontinuation. If previous tumor imaging was obtained within 4 weeks prior to the date of discontinuation, then tumor imaging at treatment discontinuation is not required. For subjects who discontinue trial treatment due to documented disease progression, this is the final required tumor imaging.

In subjects who discontinue trial treatment without documented disease progression, every effort should be made to continue monitoring disease status by tumor imaging using the same imaging schedule and modality used while on treatment (every 6 weeks [ $42 \pm 7$  days] for the first 48 weeks after randomization, then every 9 weeks [ $63 \pm 7$  days]) to monitor disease status until the start of non-study anticancer treatment, disease progression, death, or the end of the trial, whichever occurs first.

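### PFS sensitivity analysis 2: rows 1–2 and row 3 of the censoring table give the same subject opposite outcomes, and no rule says which prevails

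*Combined protocol and SAP*

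**What the plan says.** Protocol section 8.6.1.1 plans two sensitivity analyses of PFS. In the second, the text takes discontinuation of treatment or the start of a later anticancer treatment, "whichever occurs later, to be a PD event for subjects without documented PD or death". It makes no exception for missed scans. Section 3.5.1.1 of the sSAP defines the analysis in the same way.

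Table 11 (sSAP Table 1) sets out the rules. For sensitivity analysis 2:

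- Row 1, no PD or death and no new anticancer treatment: "Censored at last disease assessment if still on study therapy; progressed at treatment discontinuation otherwise".
- Row 2, no PD or death and new anticancer treatment started: "Progressed at date of new anticancer treatment".
- Row 3 is headed "No PD and no death; $\geq 2$ consecutive missed disease assessments". Its cell for this analysis censors at the last disease assessment, which is also the primary-analysis rule.

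The protocol has one tie-break: "If a subject meets multiple criteria for censoring, the censoring criterion that occurs earliest will be applied". The PFS text of the sSAP does not carry it.

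On imaging, protocol section 7.1.2.7.3 keeps subjects who stop treatment without PD on the scan schedule: "In subjects who discontinue trial treatment without documented disease progression, every effort should be made to continue monitoring disease status by tumor imaging". Scheduled imaging ends when new therapy begins; the flow chart notes in section 6.1 require it "until documented disease progression, or the start of new anti-cancer treatment". Neither PFS table defines a missed assessment.

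**The concern.** All three rows start from a subject without PD or death, and they are not mutually exclusive. Row 3 does not ask whether the subject is still on treatment or has begun new therapy. A subject who stopped treatment and then missed two scans is an event under row 1 and censored under row 3. The same clash arises between rows 2 and 3.

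Sensitivity analysis 2 is the planned check on whether the PFS result depends on censoring subjects who leave treatment or move to other therapy without documented PD. If row 3 is applied, subjects lost from imaging after leaving treatment go back to their primary-analysis status. Those who kept up their scans are counted as progressed. This runs against the purpose in the text, since subjects lost from imaging are the ones for whom informative censoring is most plausible. It also leaves a coding choice open that could be made after results are known.

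**Working it through.** **1. The plan's PFS figures reproduce.** Inputs from protocol sections 8.1, 8.8 and 8.9: 387 events, HR 0.65, one-sided alpha 0.006, 1:1 allocation, looks at 332 and 387 events.

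Fixed-design power = Φ(√(387/4) × |ln 0.65| − z₀.₉₉₄) = Φ(4.237 − 2.512) = 95.8%. With the two-look O'Brien-Fleming-type spending, power is 95.5%, nominal alphas are 0.0030 and 0.0051, and HR bounds are 0.740 and 0.770. The plan states 95.6%, and Table 15 has 0.003, 0.0051, 0.74 and 0.77. None of this depends on sensitivity analysis 2.

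**2. Two hypothetical subjects traced through the table.** Both are alive without PD at the data cutoff.

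| Subject | Primary | SA2, text and rows 1–2 | SA2, row 3 |
|---|---|---|---|
| A: last scan week 12; stops treatment before week 18; no new therapy; scans due at weeks 18 and 24 not done | Censored, week 12 | Event at discontinuation | Censored, week 12 |
| B: last scan week 18; starts new therapy before week 24; no later scans, none required | Censored, week 18 | Event at start of new therapy | Censored, week 18, only if scans no longer required count as missed |

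Subject A is a contradiction on the printed text alone. Subject B becomes one only under a broad meaning of missed. The only definition in the documents is the note to the DOR censoring table (protocol Table 12, sSAP Table 2), which includes assessments not obtained. A programmer might borrow it.

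**3. Upper bound.** With 453 subjects randomized and 387 primary PFS events, 453 − 387 = 66 subjects have neither PD nor death. Those still on study therapy with no new treatment stay censored on every reading, so the number affected lies between 0 and 66. The bound depends on reaching 387 events. A simulation with uniform accrual over 14.5 months gives about 356 events at 22 months, for which the bound would be 453 − 356 = 97. The plan used the actual enrolment pattern, which is not shown, so this does not call the 387 into question.

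**4. Illustration for subjects lost after stopping treatment.** The plan's 1% per month dropout, used as a stand-in for leaving treatment without PD, gives about 27.6 dropouts by 22 months under uniform accrual. If a share f of them has two or more consecutive missed scans and row 3 prevails, the event count is 387 + 27.6 × (1 − f):

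- f = 0 (rows 1–2 prevail): about 415
- f = 10%: about 412
- f = 50%: about 401
- f = 75%: about 394
- f = 100%: 387, the primary count

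The documents do not give f. If every dropout were a complete loss of imaging, the 6- and 9-weekly schedule puts f at about 92% (90% to 93% under other accrual shapes).

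**5. Illustration for new therapy.** Assume new therapy without PD at 2% to 4% per month, 25% of first events being deaths, and 8-month median survival after new therapy. None of these is in the documents. Simulation then gives about 26 to 45 subjects who should become events. If scans not obtained after new therapy count as missed, about 86% to 88% of them also fall in row 3. If such scans do not count as missed, this overlap largely disappears.

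**The case against.** The text defines sensitivity analysis 2 without a missed-scan exception and says that the table summarizes it. Read together, row 3 should apply only to subjects with no event under this analysis, where it keeps the primary rule. That is the sensible reading and probably the intended one, but the row 3 cell does not say so.

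A reader might infer that the tie-break decides for row 3, because the last scan precedes the event date. It does not. It ranks censoring criteria against each other, and rows 1–2 produce events here. It does not decide for rows 1–2 either.

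A reader might also infer that row 3 largely cancels the analysis by censoring most of the subjects it should reclassify. That requires row 3 to prevail. For new-therapy subjects it also requires scans that were never due to count as missed; section 7.1.2.7.2 ends imaging at "the start of a non-study anti-cancer treatment, withdrawal of consent, or death, whichever occurs first". For subjects who only stop treatment it requires a high rate of missed scans, although they remain on the imaging schedule. The documents state none of these.

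Nor do they support a particular shift in the HR, which depends on assumed new-therapy rates by arm. In simulations with somewhat different assumptions, rates of 2% (control) and 4% (pembrolizumab) per month moved the HR from 0.71 in the primary analysis to 0.76 in the intended analysis, against 0.71 under row 3. With the rates reversed it moved from 0.684 to 0.685.

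The analysis carries no alpha. The sSAP also plans an investigator-assessed PFS sensitivity analysis and allows RMST. These points limit the consequence but leave the contradiction in place.

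**Conclusion.** The point holds as a contradiction between printed rules. For a living subject without PD who has stopped treatment or begun new therapy, rows 1–2 and the text say event, and row 3 says censored once two or more consecutive assessments are missed. Nothing in either document ranks them. Following row 3 returns subjects lost from imaging to their primary-analysis status and weakens the check on informative censoring. Only if scans not obtained after new therapy were also counted as missed would most of the intended reclassification be lost.

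The size cannot be derived from the documents. It is bounded by 66 subjects if 387 PFS events occur, and could be close to none. The event counts in the working rest on uniform accrual, exponential times and dropout as a proxy, and the new-therapy counts on assumed rates. The primary PFS test, its alpha and its power are unaffected. The correction is worth making because it is specific, nearly free and brings the table into line with the plan's own text.

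**What to change.** In protocol Table 11 and sSAP Table 1, change the row 3 cell for sensitivity analysis 2 to: *Still on study therapy and no new anticancer treatment: censored at last disease assessment. Otherwise: progressed as in rows 1–2.* Add a note to both tables that scans no longer required after the start of new anticancer treatment are not missed assessments.

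The cost is one cell and one sentence in each document, with no change to data collection or to the primary analysis. The downside is that the sensitivity HR may look slightly less favourable than it would with row 3 applied.

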### 8.6.1.2 Overall Survival

The non-parametric Kaplan-Meier method will be used to estimate the survival curves. The treatment difference in survival will be assessed by the stratified log-rank test (based on the stratification factor defined in Section 5.4). A stratified Cox proportional hazard model with Efron's method of tie handling will be used to assess the magnitude of the treatment difference (ie, the HR). The HR and its 95% CI from the stratified Cox model with a single treatment covariate will be reported. The stratification factors used for randomization (See Section 5.4) will be applied to both the stratified log-rank test and the stratified Cox model. Restricted Mean Survival Time (RMST) method may be conducted for OS to account for the possible non-proportional hazards effect.

Since subjects in the placebo+EP arm are expected to discontinue from the study earlier compared to subjects in the pembrolizumab arm because of earlier onset of PD and may switch to another anti PD-1 treatment following confirmation of PD, adjustment for the effect of crossover on OS may be performed based on recognized methods, (eg, the Rank Preserving Structural Failure Time (RPSFT) model proposed by Robins and Tsiatis [115]), based on an examination of the appropriateness of the data to the assumptions required by the method used.

### 8.6.1.3 Objective Response Rate

The ORR is defined as the proportion of subjects who achieve a best objective response of PR or CR.

Stratified Miettinen and Nurminen’s method will be used for comparison of ORR between the treatment groups. The difference in ORR and its 95% CI from the stratified Miettinen and Nurminen method with strata weighting by sample size will be provided. The same stratification factors used for randomization (see Section 5.4) will be used as stratification factors in the analysis.

### 8.6.1.4 Duration of Response

For subjects who demonstrate CR or PR, DOR is defined as the time from first documented evidence of CR or PR until disease progression or death due to any cause, whichever occurs first. Censoring rules for DOR are summarized in [Table 12](#). DOR will be assessed by BICR per RECIST 1.1 modified to follow a maximum of 10 target lesions and a maximum of 5 target lesions per organ.

For each DOR analysis, a corresponding summary of the reasons responding subjects are censored will also be provided. Subjects who are alive, have not progressed, have not initiated new anti-cancer treatment, have not been determined to be lost to follow-up, and have had a disease assessment within ~ 5 months of the data cutoff date are considered ongoing responders at the time of analysis. If a subject meets multiple criteria for censoring, the censoring criterion that occurs earliest will be applied.

Table 12 Censoring Rules for Duration of Response

Situation	Date of Progression or Censoring	Outcome
No progression nor death, no new anti-cancer therapy initiated	Last adequate disease assessment	Censor (non-event)
No progression nor death, new anti-cancer therapy initiated	Last adequate disease assessment before new anti-cancer therapy initiated	Censor (non-event)
Death or progression after $\geq 2$ consecutive missed disease assessments	Last adequate disease assessment prior to $\geq 2$ missed adequate disease assessments	Censor (non-event)
Death or progression after $\leq 1$ missed adequate disease assessments	Progressive disease or death	End of response (Event)
Note: A missed disease assessment includes any assessment that is not obtained or is considered inadequate for evaluation of response.		

A summary of the primary analysis strategy for the primary and secondary efficacy endpoints is provided in [Table 13](#).

Table 13 Efficacy Analysis Methods for Primary and Secondary Efficacy Endpoints

Endpoint/Variable (Description, Time Point)	Statistical Method	Analysis Population	Missing Data Approach
Primary Analyses:			
PFS (RECIST 1.1*) by BICR	Testing: Stratified Log-rank test Estimation: Stratified Cox model with Efron's tie handling method	ITT	Censored according to rules in Table 11
OS	Testing: Stratified Log-rank test Estimation: Stratified Cox model with Efron's tie handling method	ITT	Censored at last known alive date
Secondary Analyses:			
ORR (RECIST 1.1*) by BICR	Testing: Stratified Miettinen and Nurminen method	ITT	Subjects with missing data are considered non-responders
DOR (RECIST 1.1*) by BICR	Summary statistics using Kaplan-Meier method	All responders in ITT	Non-responders are excluded in analysis
*As assessed by BICR per RECIST 1.1 modified to follow a maximum of 10 target lesions and a maximum of 5 target lesions per organ			

### 8.6.2 Statistical Methods for Safety Analyses

Safety and tolerability will be assessed by clinical review of all relevant parameters including AEs and laboratory tests.

The analysis of safety results will follow a tiered approach ([Table 14](#)). The tiers differ with respect to the analyses that will be performed. Safety parameters or AEs of special interest that are identified a priori constitute “Tier 1” safety endpoints that will be subject to inferential testing for statistical significance with p-values and 95% CIs provided for between-group comparisons. Other safety parameters will be considered Tier 2 or Tier 3. Tier 2 parameters will be assessed via point estimates with 95% CIs provided for between-group comparisons; only point estimates by treatment group are provided for Tier 3 safety parameters.

Adverse events of special interest (AEOSIs) that are immune-mediated or potentially immune-mediated are well documented and will be evaluated separately; however, these events have been characterized consistently throughout the pembrolizumab clinical development program and determination of statistical significance is not expected to add value to the safety evaluation. Further, pembrolizumab added to platinum doublets studied thus far have not been found to impact safety, and in an ongoing Phase 1 clinical trial, the chemotherapeutic regimen used here with pembrolizumab has not led to increased toxicity

(NCT02402920). Additionally, there are no known AEs associated with subjects with SCLC for which determination of a p-value is expected to impact the safety assessment. For these reasons, there are no events of interest that warrant inferential testing. Therefore, there are no Tier I events in this study.

Adverse experiences (specific terms as well as system organ class terms) that are not pre-specified as Tier-1 endpoints will be classified as belonging to "Tier 2" or "Tier 3", based on the number of events observed. Membership in Tier 2 requires that at least 10% of subjects in any treatment group exhibit the event; all other AEs and predefined limits of change will belong to Tier 3.

The threshold of at least 10% was chosen for membership in Tier 2 because subjects enrolled in this study are in critical condition and usually experience various AEs of similar types regardless of treatment, events reported less frequently than in 10% of subjects would obscure the assessment of the overall safety profile and add little to the interpretation of potentially meaningful treatment differences. In addition, Grades 3 to 5 AEs ( $\geq 5\%$  of subjects in one of the treatment arms) and SAEs ( $\geq 5\%$  of subjects in one of the treatment arms) will be considered Tier 2 events. For Tier 2 events, 95% CIs will be provided for between-treatment differences in the percentage of subjects with events; these analyses will be performed using the Miettinen and Nurminen method [116], an unconditional, asymptotic method. Because many 95% CIs may be provided without adjustment for multiplicity, the CIs should be regarded as a helpful descriptive measure to be used in safety review, not a formal method for assessing the statistical significance of the between-treatment differences.

For laboratory parameters, the number and percentage of subjects with increases from baseline in laboratory test toxicity grades based on the highest post-baseline toxicity grade and shift of toxicity grade from baseline to the worst post-baseline toxicity grade will be summarized by treatment arm.

Table 14 Analysis Strategy for Safety Parameters

Safety Tier	Safety Endpoint	95% CI for Treatment Comparison	Descriptive Statistics
Tier 2	Any AE ( $\geq 10\%$ of subjects in one of the treatment arms)	X	X
	Any Grades 3 to 5 AE ( $\geq 5\%$ of subjects in one of the treatment arms)	X	X
	Any serious AE ( $\geq 5\%$ of subjects in one of the treatment arms)	X	X
Tier 3	Any AE		X
	Any change from baseline results (laboratory tests)		X

Abbreviations: AE=adverse event, CI=confidence interval

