#### **4.2.3.3 Safety Endpoints**

The incidence of AE/SAEs (including fatal SAEs), immune-related AEs, laboratory abnormalities, and rates of dose interruption and discontinuation due to AEs are important endpoints for safety and tolerability evaluations.

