### 3.5.2 Statistical Methods for Safety Analyses

Safety and tolerability will be assessed by clinical review of all relevant parameters including AEs and laboratory tests.

The analysis of safety results will follow a tiered approach ([Table 4](#)). The tiers differ with respect to the analyses that will be performed. Safety parameters or AEs of special interest that are identified a priori constitute “Tier 1” safety endpoints that will be subject to inferential testing for statistical significance with p-values and 95% CIs provided for between-group comparisons. Other safety parameters will be considered Tier 2 or Tier 3. Tier 2 parameters will be assessed via point estimates with 95% CIs provided for between-group comparisons; only point estimates by treatment group are provided for Tier 3 safety parameters.

Adverse events of special interest (AEOSIs) that are immune-mediated or potentially immune-mediated are well documented and will be evaluated separately; however, these events have been characterized consistently throughout the pembrolizumab clinical development program and determination of statistical significance is not expected to add value to the safety evaluation. Further, pembrolizumab added to platinum doublets studied thus far have not been found to impact safety, and in an ongoing Phase 1 clinical trial, the chemotherapeutic regimen used here with pembrolizumab has not led to increased toxicity (NCT02402920). Additionally, there are no known AEs associated with subjects with SCLC for which determination of a p-value is expected

to impact the safety assessment. For these reasons, there are no events of interest that warrant inferential testing. Therefore, there are no Tier I events in this study.

Adverse experiences (specific terms as well as system organ class terms) that are not pre-specified as Tier-1 endpoints will be classified as belonging to "Tier 2" or "Tier 3", based on the number of events observed. Membership in Tier 2 requires that at least 4 subjects in any treatment group exhibit the event; all other AEs and predefined limits of change will belong to Tier 3.

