The threshold of at least 10% was chosen for membership in Tier 2 because subjects enrolled in this study are in critical condition and usually experience various AEs of similar types regardless of treatment, events reported less frequently than in 10% of subjects would obscure the assessment of the overall safety profile and add little to the interpretation of potentially meaningful treatment differences. In addition, Grades 3 to 5 AEs ( $\geq 5\%$  of subjects in one of the treatment arms) and SAEs ( $\geq 5\%$  of subjects in one of the treatment arms) will be considered Tier 2 events. For Tier 2 events, 95% CIs will be provided for between-treatment differences in the percentage of subjects with events; these analyses will be performed using the Miettinen and Nurminen method, an unconditional, asymptotic method. Because many 95% CIs may be provided without adjustment for multiplicity, the CIs should be regarded as a helpful descriptive measure to be used in safety review, not a formal method for assessing the statistical significance of the between-treatment differences.

For laboratory parameters, the number and percentage of subjects with increases from baseline in laboratory test toxicity grades based on the highest post-baseline toxicity grade and shift of toxicity grade from baseline to the worst post-baseline toxicity grade will be summarized by treatment arm.

Table 4 Analysis Strategy for Safety Parameters

Safety Tier	Safety Endpoint	95% CI for Treatment Comparison	Descriptive Statistics
Tier 2	Any AE ( $\geq 10\%$ of subjects in one of the treatment arms)	X	X
	Any Grades 3 to 5 AE ( $\geq 5\%$ of subjects in one of the treatment arms)	X	X
	Any serious AE ( $\geq 5\%$ of subjects in one of the treatment arms)	X	X
Tier 3	Any AE		X
	Any change from baseline results (laboratory tests)		X

Abbreviations: AE=adverse event, CI=confidence interval

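### No between-arm interval is guaranteed for an immune-mediated adverse event below 10% of an arm (5% if Grade 3-5 or serious), and the sSAP states two different thresholds

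*Combined protocol and SAP*

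**What the plan says.** Protocol Section 8.6.2 sorts safety parameters into tiers. Tier 1 events, named in advance, would get p-values and intervals. For immune-mediated adverse events of special interest (AEOSIs), the section says that they are well documented and will have their own evaluation, but that "determination of statistical significance is not expected to add value to the safety evaluation". It concludes: "Therefore, there are no Tier I events in this study".

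All adverse events not named as Tier 1, both specific terms and system organ class terms, are then placed by frequency: "Membership in Tier 2 requires that at least 10% of subjects in any treatment group exhibit the event; all other AEs" fall to Tier 3. Grade 3-5 events and serious events enter Tier 2 at 5% of an arm. Tier 2 gets a Miettinen-Nurminen 95% interval for the between-arm difference. For the rest, "only point estimates by treatment group are provided for Tier 3 safety parameters". Table 14 repeats these thresholds.

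Section 3.5.2 of the sSAP carries the same text with one difference: "Membership in Tier 2 requires that at least 4 subjects in any treatment group exhibit the event". Its next paragraph opens with "The threshold of at least 10% was chosen for membership in Tier 2", and sSAP Table 4 also uses 10% and 5%.

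Protocol Section 4.2.3.3 says of the safety endpoints that "immune-related AEs, laboratory abnormalities, and rates of dose interruption and discontinuation due to AEs are important endpoints for safety and tolerability evaluations".

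**The concern.** The reason for leaving AEOSIs out of Tier 1 is that significance testing would add nothing. That is a reason to omit p-values. It is not a reason to omit an estimate of the difference with its uncertainty, and Section 8.6.2 itself describes its Tier 2 intervals as descriptive. The reason for the 10% cut-off is that these patients have many similar adverse events whichever treatment they receive. That suits chemotherapy and disease toxicity better than events that Section 5.2.1.2.1 ties to pembrolizumab exposure.

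At stake is how clearly the trial reports the immune toxicity that pembrolizumab adds to etoposide/platinum. As written, frequent events are assured a between-arm interval. A less frequent immune-mediated event is not, even where the two arms differ clearly. The conflicting sSAP threshold means that two programmers could build different Tier 2 tables from the same document.

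**Working it through.** The documents attach no power or precision figure to the safety tiers, so there is no stated figure to reproduce. The check turns the thresholds into counts and computes the intervals that fall just under them.

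**Inputs.** 453 subjects randomized 1:1 (Sections 8.1 and 5.3), so 453 / 2 = 226.5, taken as 226 per arm. The safety population is the treated subjects (Section 8.5.2). Its size is not given, and I assume it is close to the number randomized. Interval method: Miettinen-Nurminen, unstratified.

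**Thresholds as counts.**
- 10%: 0.10 × 226 = 22.6, so 23 subjects are needed. The largest count left out is 22 (22/226 = 9.7%).
- 5%: 0.05 × 226 = 11.3, so 12 are needed. The largest count left out is 11 (11/226 = 4.9%).
- sSAP text: 4 subjects, 4/226 = 1.8%.

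**Interval.** The limits are the values d at which |z(d)| = 1.96, with z(d) = (p1 − p2 − d) / √{[r1(1 − r1)/n1 + r2(1 − r2)/n2] × N/(N − 1)}. Here r1 and r2 are the maximum likelihood estimates under r1 − r2 = d, and N = n1 + n2.

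**Results (hypothetical counts, 226 per arm).**

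| Events, pembrolizumab vs placebo | Difference, points | 95% CI |
|---|---|---|
| 22 vs 4, any grade | 18/226 = 8.0 | 4.0 to 12.7 |
| 11 vs 1, Grade 3-5 | 10/226 = 4.4 | 1.8 to 8.1 |
| 11 vs 3, Grade 3-5 | 8/226 = 3.5 | 0.4 to 7.3 |
| 11 vs 4, Grade 3-5 | 7/226 = 3.1 | −0.2 to 7.0 |
| 7 vs 1 | 6/226 = 2.7 | 0.3 to 5.9 |
| 7 vs 2 | 5/226 = 2.2 | −0.5 to 5.5 |
| 6 vs 1 | 5/226 = 2.2 | −0.1 to 5.3 |

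Under the 10%/5% rule none of these rows is assured an interval. Under the sSAP's 4-subject wording all of them would have one.

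**Chance that the pembrolizumab arm reaches Tier 2.** The documents give no incidence for individual immune-related events with this combination, so the true rate is an assumption, shown over a range. With X binomial on about 226 subjects:
- Any grade, P(X ≥ 23): 0.1% at a true rate of 5%; 14% at 8%; about one half at 10%; 83% at 12%; 99% at 15%.
- Grade 3-5 or serious, P(X ≥ 12): 0.2% at 2%; 4% at 3%; 46% at 5%.

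**Coverage of the endpoints in Section 4.2.3.3.** Table 14 has no row specific to immune-related events. They enter through the general rows, subject to the thresholds. Fatal events are Grade 5 and serious, so the Grade 3-5 and serious rows cover them, subject to 5%. Discontinuation and interruption due to adverse events have no row at all.

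**The case against.** A reader might infer that most of pembrolizumab's characteristic toxicities will be reported without an interval. The documents do not support that. They give no incidences, so the share affected is unknown, and any event above the thresholds gets its interval. System organ class terms can also reach Tier 2, although they do not isolate immune-mediated events.

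A reader might also infer that the plan refuses intervals for AEOSIs. It does not. It promises a separate evaluation and leaves the content open, and that evaluation could include intervals. This is a gap in specification. The sSAP's optional exposure-adjusted summary does not close it, since it names no interval.

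A reader might conclude that a several-fold excess would always have been resolved by an interval. The table shows otherwise: 11 vs 4, 7 vs 2 and 6 vs 1 all include zero. In any case, whether zero is excluded is not the purpose of an interval that the plan calls descriptive.

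The strongest remaining objection is that little is lost. The safety objective in Section 3.2 concerns the profile in each arm, both arms' estimates are reported, and a reader with the denominators can compute the unstratified interval. That stands, and it limits the weight of the point. It does not answer the mismatch between the stated reason and the omission, nor the sSAP's two thresholds.

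**Conclusion.** The point holds as a reporting and specification gap. No between-arm interval is assured for an immune-mediated event seen in up to 22 subjects of an arm, or up to 11 if Grade 3-5 or serious, under the rule in the protocol and sSAP Table 4. The rationale given argues only against testing. The sSAP contradicts itself on the threshold by a wide margin, 4 subjects against 23, so the rule in force has to be settled in any case.

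The conclusion assumes about 226 treated subjects per arm; a few untreated subjects would move the cut-offs by at most about one subject. The counts in the examples are illustrations, not predictions. No data are lost, and efficacy conclusions and error control are unaffected.

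**What to change.** In protocol Section 8.6.2 and Table 14, and in sSAP Section 3.5.2 and Table 4:
- List the AEOSI categories in advance and state what their separate evaluation contains.
- Report the between-arm difference with its Miettinen-Nurminen 95% interval and no p-value, regardless of frequency, for any AEOSI, each AEOSI category, Grade 3-5 AEOSIs, fatal adverse events, and adverse events leading to discontinuation or to interruption.
- Keep a single frequency rule for all other terms, and correct the 4-subject sentence in the sSAP to match it.

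The cost is wording and a few table rows, with no new data and no alpha. The downside is a few more unadjusted descriptive intervals, some of them wide. Section 8.0 already provides for recording changes to non-confirmatory analyses in the sSAP if they are made before any analysis is conducted.
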